### **6.3.4 Cardiac Monitoring**

Left ventricular ejection fraction (LVEF) assessed via echocardiogram and 12-lead ECGs

are required to be performed as scheduled; ECG shall be performed pre-dose and at 3 hours ( $\pm$  15 minutes) post fruquintinib dose on Days 1 and 15 in Cycle 1. ECG will be conducted on Day 1 of each cycle from Cycle 2 and onward. QTcF interval should be calculated and be closely monitored. See [Appendix A](#). MUGAs are permitted if echocardiograms cannot be performed.

Test results will be reviewed by the investigator to determine patient eligibility at screening. Additional tests and other cardiac monitoring should be performed as clinically indicated during the study.

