8. Hematology consists of complete blood count, including red blood cell count, hemoglobin, hematocrit, reticulocyte count, white blood cell count with differential (neutrophils, bands, lymphocytes, eosinophils, monocytes, basophils, and other cells), and platelet count.
9. The chemistry panel includes blood urea nitrogen, creatinine and creatinine clearance, sodium, potassium, chlorine, bicarbonate, calcium, magnesium, phosphorus, glucose, alanine aminotransferase, bilirubin (total), aspartate aminotransferase, alkaline phosphatase, lactate dehydrogenase, total cholesterol, triglycerides, uric acid, protein (total) and albumin.
10. Urinalysis includes pH, glucose, protein, and blood. A 24-hour urine should be collected from all patients with  $>1+$  proteinuria for quantitative test of urine protein during the screening. If protein  $\geq 2+$  during the period of study treatment, a 24-hour urine test should be conducted within 1 week.
11. MUGAs are permitted if echocardiograms cannot be performed.
12. Includes free T3, free T4, and thyroid-stimulating hormone (TSH).
13. Women of childbearing potential will receive a serum pregnancy test during screening and within 30 days after treatment completion, and a urine pregnancy test on Day 1 of each 28-day cycle beginning at Cycle 2. If pregnancy is suspected, additional tests should be completed. In the case of menopausal women, the date of menopause onset should be recorded.
14. CA125 level for patients with ovarian cancer, PSA for patients with prostate cancer, or other tumor markers (as appropriate) should be obtained as clinically indicated or with each tumor assessment.
15. On Days 1 and 15 in Cycle 1, ECG should be performed at pre-dose and at 3 hours ( $\pm 15$  minutes) post-dose (around  $C_{max}$  after single dose and at steady state in order to evaluate concentration-QT relationship for fruquintinib). Untimed ECG will be conducted on Day 1 of each cycle from Cycle 2 and onward.
16. After informed consent, all SAEs and concomitant medications will be collected. After initiation of study drug, all AEs and SAEs will be collected until 30 days following the last dose of study drug or a new treatment of anti-tumor therapy, whichever is earlier. After this period, investigators should report only SAEs that are considered to be related to the study drug.

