5.4. WINDOWING CONVENTIONS

The visit-window mapping is described in [APPENDIX 4](#). Visit-based summaries will be based on the windowed visits. All data, whether or not within the visit windows, will be presented in listings.

For windowed visits during the treatment cycles,

- If more than 1 assessment occurs during a visit window, the assessment closest to the scheduled day will be assigned to the windowed visit.
- If two assessments are equidistant from the scheduled day, the later assessment will be assigned to the windowed visit.
- If there are multiple assessments on the same day, the worst case will be used.

For the post-treatment visit, the last assessment in the window will be included in the summary. The window for the post-treatment visit will be "from the last dose date + 8 days to the last dose date + 37 days".

For a patient who prematurely discontinues the study, the premature visit will be slotted accordingly.

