17.5. ECG EVALUATIONS

Results of the Electrocardiogram (ECG) will be included in the reporting of this study. Overall assessment of ECG up to 37 days following the date of last dose of study medication will be included for analysis.

The following ECG parameters will be reported for this study:

Document: [REDACTED]

Author: [REDACTED]

Version Number: 2.5

Version Date: 18Feb2022

Template No.: [REDACTED]

Reference: CS_WI_BS005

Effective Date: 02Dec2019

- Heart Rate (bpm)
- PR Interval (msec)
- QT Interval (msec)
- QRS Interval (msec)
- RR Interval (msec)
- QTcF Interval (msec)

Overall assessment of ECG (Investigator’s judgment): Normal, NCS, CS.

The following summaries will be provided for ECG data:

- Observed and change from baseline by visit
- Markedly abnormal value and change of ECG by visit
- Shift table of change from baseline to worst post-baseline ECG assessment by investigator

Listing of ECG data (Assessment date, Timepoint, HR, PR interval, QT interval, QRS interval, RR interval, QTcF interval) by patients, with results which meet the markedly abnormal criteria being flagged.

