11. MUGAs are permitted if echocardiograms cannot be performed.
12. Includes free T3, free T4, and thyroid-stimulating hormone (TSH).
13. Women of childbearing potential will receive a serum pregnancy test during screening and within 30 days after treatment completion, and a urine pregnancy test on Day 1 of each 28-day cycle beginning at Cycle 2. If pregnancy is suspected, additional tests should be completed. In the case of menopausal women, the date of menopause onset should be recorded.
14. CA125 level for patients with ovarian cancer, PSA for patients with prostate cancer, or other tumor markers (as appropriate) should be obtained as clinically indicated or with each tumor assessment.
15. On Days 1 and 15 in Cycle 1, ECG should be performed at pre-dose and at 3 hours (± 15 minutes) post-dose (around C_{max} after single dose and at steady state in order to evaluate concentration-QT relationship for fruquintinib). Untimed ECG will be conducted on Day 1 of each cycle from Cycle 2 and onward.
16. After informed consent, all SAEs and concomitant medications will be collected. After initiation of study drug, all AEs and SAEs will be collected until 30 days following the last dose of study drug or a new treatment of anti-tumor therapy, whichever is earlier. After this period, investigators should report only SAEs that are considered to be related to the study drug.
17. **For subjects in Expansion Cohorts B, C, D, and E** - Survival follow-up (by telephone) should be performed every 12 (± 2) weeks from the date of the Treatment Completion visit. All subsequent anti-tumor therapy and information about ongoing or unresolved study drug-related SAEs will be collected. For the patients that discontinue the study without PD, all available tumor assessment results during survival follow-up will be recorded in the CRF until confirmation of PD. The date and cause of death should be recorded, if applicable. Patients who withdraw consent are encouraged to be followed for survival. If the patient has clearly expressed his/her refusal to be followed after withdrawal of consent, he/she will terminate the study and no survival follow-up will be performed.

Document:

Author:

Version Number:

2.5

Version Date:

18Feb2022

Template No.:

Reference: CS_WI_BS005

Effective Date: 02Dec2019

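### The SAP's same-day worst-case rule reduces the planned pre-dose and 3 h ECGs on Cycle 1 Day 15 to one selected value in the by-visit change-from-baseline summary

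*SAP*

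**What the plan says.** **What is measured.** Protocol Appendix A, note 15, states: "On Days 1 and 15 in Cycle 1, ECG should be performed at pre-dose and at 3 hours". Protocol 6.3.4 repeats the pair ("ECG shall be performed pre-dose and at 3 hours"), and so does the schedule reproduced in SAP Appendix 1 ("ECG should be performed at pre-dose and at 3 hours"). Note 15 gives the reason, which is to sample near Cmax after a single dose and at steady state, "in order to evaluate concentration-QT relationship for fruquintinib". From Cycle 2 onward it plans one untimed ECG on Day 1 of each cycle.

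**How it is summarised.** SAP 17.5 lists "Observed and change from baseline by visit" among the ECG summaries and names time point only for the patient listing. SAP 5.4 says "Visit-based summaries will be based on the windowed visits" and then gives the selection rules for windowed visits during treatment cycles. One is "If there are multiple assessments on the same day, the worst case will be used". Another is "If two assessments are equidistant from the scheduled day, the later assessment will be assigned to the windowed visit". Neither exempts ECG.

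**How visits are mapped.** SAP Appendix 4 gives 12-lead ECG one Day 1 window and one C1D15 window running from Day 2 to three days before the end of the cycle. Neither window is split by time point. SAP Appendix 2 has one output label for C1D15.

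**Baseline.** SAP 5.2 takes the last non-missing reading before treatment. It uses the time point on the ECG form to place the Day 1 3 h ECG after baseline.

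**The concern.** Keeping the worst of several values suits a shift table or a threshold count, where the question is whether anything bad happened. It does not suit a mean. The Day 15 ECGs are two planned measurements under different conditions, not accidental repeats. Picking one of them by its value has two effects.

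- The C1D15 mean change compares a selected reading with an unselected baseline, so it can move away from zero with no drug effect. Later cycles have one planned ECG each and carry no such selection. Part of any difference between Day 15 and later visits could then be produced by the rule.
- The retained reading is pre-dose in some patients and 3 h post-dose in others. The row describes neither time point, and the steady-state contrast between them is lost from the summary.

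**Working it through.** The documents give no QTcF variance and no figure on this point, so there is nothing to reproduce. The check has two parts: what the text does to the Day 15 pair, and how large the effect could be.

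**1. The rule applied to Day 15**

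| Step | Source | Result |
|---|---|---|
| Two ECGs planned on the same day | Protocol 6.3.4; Appendix A note 15 | pre-dose and 3 h |
| Map to a visit | SAP Appendix 4 | both fall in C1D15 |
| Choose one for the visit summary | SAP 5.4, same-day rule | the worst |
| Subtract baseline | SAP 5.2 | one reading, not chosen by value |
| Report | SAP 17.5 | one C1D15 row |

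**2. Size**

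Assumptions, none of them in the documents: worst means the higher QTcF; readings are normal with within-patient SD s; the two readings have correlation r; d is the true 3 h minus pre-dose difference. Let m be the patient's pre-dose mean and t = s√(2(1−r)) the SD of the difference. Then

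E[larger reading] − m = d·Φ(d/t) + t·φ(d/t).

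With d = 0 this becomes t/√(2π) = s√((1−r)/π). For s = 8:

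- r = 0: 8 × √(1/π) = 8 × 0.564 = 4.5 msec
- r = 0.5: 8 × √(0.5/π) = 8 × 0.399 = 3.2 msec
- r = 0.8: 8 × √(0.2/π) = 8 × 0.252 = 2.0 msec

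At r = 0 the bias is 2.8 msec for s = 5 and 6.8 msec for s = 12. Two ECGs about three hours apart share that day's variation, so r = 0 is better read as the upper end of the range.

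With a true post-dose rise, at r = 0:

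| s (msec) | d (msec) | Reported mean minus 3 h mean | Reported mean minus pre-dose mean | Pre-dose reading kept |
|---|---|---|---|---|
| 5 | 5 | 1.00 | 6.00 | 24% |
| 8 | 5 | 2.45 | 7.45 | 33% |
| 12 | 5 | 4.56 | 9.56 | 38% |
| 5 | 10 | 0.25 | 10.25 | 8% |
| 8 | 10 | 1.17 | 11.17 | 19% |
| 12 | 10 | 2.91 | 12.91 | 28% |

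For s = 8 and d = 5: t = 11.31 and d/t = 0.442, so 5 × 0.671 + 11.31 × 0.362 = 7.45. A simulation of one million pairs also gave 7.45. The excess over the 3 h mean shrinks as the true rise grows. With separate rows the selection bias is zero at each time point and d can be read directly.

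**The case against.** **Worst is undefined, so the direction is assumed.** This stands. SAP 17.5.2 flags QTcF both ways: above 450, 480 and 500 msec and at or below 300, with increases and decreases. Higher is the natural reading for QTcF, but the SAP does not say so. The gap needs closing in its own right.

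**The equidistance rule could govern.** Two ECGs on one day are equally far from the scheduled day, and that rule would keep the later one, the 3 h reading. There would then be no selection by value, though the pre-dose reading would still drop out of the table. The same-day rule is the more specific and is the one to apply; at the least, the two bullets need an order of precedence.

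**The concentration-QT question is answered elsewhere.** The SAP Introduction puts PK and pharmacodynamic analyses outside the document, and both readings stay in the listing with their time point. This limits the consequence: no data are lost. It does not correct the by-visit table that the SAP does specify.

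**The table shells may add time-point rows.** They are not among the documents, so this cannot be excluded. The SAP text does not provide for it.

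**The error is conservative and the tables are descriptive.** If worst means higher, the bias overstates QTcF prolongation. SAP 5.5 plans no hypothesis tests. Both points lower the stakes, but a mean change that depends on a selection rule is still not the quantity its label describes.

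**A stronger reading on Day 1.** A reader might infer that C1D1 change is the larger of pre-dose and 3 h minus pre-dose, and so can never be negative. The documents do not support this. SAP 5.2 makes the pre-dose ECG baseline and the 3 h ECG post-baseline, and SAP Appendix 2 lists Baseline and C1D1 as separate visits. The 3 h ECG is the only planned post-baseline reading that day, so the effect near Cmax after a single dose may well be readable from C1D1.

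**Conclusion.** The point holds for Day 15 and only there. As written, the SAP reduces two planned ECGs to one selected value in the by-visit summary and compares it with a single-reading baseline. If worst means the higher QTcF and there is no true pre/post difference, the mean change is too high by s√((1−r)/π), which is about 2.0 to 4.5 msec for an assumed s of 8 msec and r between 0.8 and 0. These figures illustrate the size and are not estimates from the trial. A reader might infer that the tables will show a Day 15 rise that fades in later cycles. That could happen, but it depends on s, r, the true drug effect and the meaning of worst, none of which the documents settle. What follows from the text alone is narrower: the C1D15 row cannot show the steady-state pre-dose versus 3 h contrast. The harm is limited to descriptive safety tables, and no efficacy result is touched. The change is worth making because it is cheap and the ECG form already records the time point.

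**What to change.** In SAP 5.4, 17.5 and Appendix 4, state that the planned Cycle 1 ECGs are summarised by visit and nominal time point: Day 1 pre-dose (baseline), Day 1 3 h, Day 15 pre-dose and Day 15 3 h. Each post-baseline time point gets its own change from baseline.

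Keep the worst-case rule for unplanned same-day repeats and for the shift and markedly abnormal summaries. It should not be removed from 5.4 altogether, because laboratory tests, vital signs and unplanned ECG repeats would then have no same-day selection rule. Define worst for each ECG parameter, including its direction, and say that the same-day rule takes precedence over the equidistance rule.

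The cost is extra time-point rows for the six ECG parameters and a revised Appendix 4 mapping. No new data are needed.

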## 6.5 Study Completion/Early Termination Visit

Patients who complete the study or discontinue study drug will be asked to return to the

clinic at 30 ( $\pm$  7) days after the decision to permanently discontinue treatment with fruquintinib. Ongoing AEs will be followed until the event has resolved to baseline grade, the event is assessed as stable by the investigator, new anti-tumor treatment is initiated, the patient is lost to follow-up, the patient withdraws consent, or when it has been determined that the study treatment or participation is not the cause of the AE.

Please see the Study Flowchart provided in [Appendix A](#) for assessments to be performed at the study completion or early termination visit.

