Date Procedure	Screening		Treatment 							Treatment Completion 	Follow-up
			Cycle 1				Cycle 2-3		Cycle 4 and onwards		
	Day -28 to Day -1	Day -7 to Day -1	Day 1	Day 8 (±1d)	Day 15 (±1d)	Day 22 (±1d)	Day 1 (±3d)	Day 15 (±3d)	Day 1 of each subsequent cycle (±3d)	30 (±7) days after permanent treatment discontinuation	Every 12 (±2) weeks from Treatment Completion Visit
			specific timepoints								
Adverse event 	X	X	X	X	X	X	X	X	X	X	
Fruquintinib treatment			Once daily, 3 weeks on/ 1 week off								
Survival follow up 											X

Note:

1. A written informed consent form should be obtained prior to any protocol-specific procedure or test. Tests completed within 28 days prior to enrollment can be used for screening and do not need to be repeated (except hematology, coagulation test, clinical chemistry, or urinalysis results).
2. Unless otherwise indicated, the visit window during the treatment period will be ± 3 days (± 1 day during cycle 1).
3. Patients who complete or prematurely discontinue the study need to return to the study site for a follow-up at 30 (±7) days after the decision to discontinue treatment permanently. Ongoing AEs will be followed until the event has resolved to baseline grade, the event is assessed as stable by the investigator, new anti-tumor treatment is initiated, the patient is lost to follow-up, the patient withdraws consent, or when it has been determined that the study treatment or participation is not the cause of the AE.
4. The treatment completion visit tumor assessment can be omitted if treatment ended because of disease progression or the patient had a tumor assessment within 14 days prior to the last dose of study drug.
5. Concomitant medication includes any prescribed or over-the-counter medicines. All medication used by patients within 7 days before screening and 30 days after study treatment completion should be recorded. At each visit, all medication used since the prior visit should be recorded.

6. Vital signs include blood pressure, heart rate, respiratory rate, and temperature. For patient with a baseline history of antihypertensive medications, blood pressure should be monitored at 3 hours ( $\pm 2$  hours) after the daily doses of anti-hypertensive medication.
7. Please refer to Section 6.3.2 for the assessments that should be completed as part of the Complete and Limited Physical Exams.

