17.4. LABORATORY EVALUATIONS

Results from the local laboratory will be included in the reporting of this study for Hematology, Serum chemistry, Coagulation, Urinalysis, 24-hours urine protein, and Thyroid function test.

Document: [REDACTED]

Author: [REDACTED]

Version Number:

2.5

Version Date:

18Feb2022

Template No.: [REDACTED]

Reference: CS_WI_BS005

Effective Date: 02Dec2019

Indexes collected for laboratory assessments are shown in table below:

Laboratory Test	Parameters
Hematology	red blood cell [RBC] count, hemoglobin, platelet count, white blood cell [WBC], neutrophils, lymphocytes, monocytes, eosinophils, basophils, hematocrit, reticulocyte count
Coagulation	activated partial thromboplastin time [aPTT], international normalized ratio [INR]
Serum chemistry	total protein, albumin, glucose, blood urea nitrogen [BUN], creatinine, creatinine clearance, alkaline phosphatase [ALP], lactate dehydrogenase [LDH], total bilirubin, Aspartate Aminotransferase [AST], Alanine Aminotransferase [ALT], calcium, magnesium, potassium, sodium, chloride, total cholesterol, triglycerides, uric acid, bicarbonate, phosphorus
Urinalysis	pH, glucose, protein, and blood
Thyroid function	thyroid stimulating hormone [TSH], free T3, and free T4

The non-protocol specified tests and urinalysis results will not be summarized; they will only be included in listings. Data recorded by the laboratory will be converted to the International System of Units (SI) and all presentations will use SI units. Quantitative laboratory measurements reported as “< X”, i.e., below the lower limit of quantification (LLQ), or “> X”, i.e., above the upper limit of quantification (ULQ), will be converted to X for the purpose of quantitative summaries, but will be presented as recorded, i.e., as “< X” or “> X” in the listings. Quantitative data collected between after date of ICF and up to 37 days following the last dose of study medication will be used for analysis. The following summaries will be provided for laboratory data:

- Observed value and change from baseline by visit (for quantitative measurements)
- Shift from baseline to worst post-baseline CTCAE toxicity for laboratory abnormalities
- Shift from baseline to the worst post-baseline investigators’ assessment (i.e., normal, abnormal but not clinically significant [NCS], abnormal and clinically significant [CS] for quantitative measurements and categorical measurements)

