Note: The end date of a cycle (EOC) is defined as the one day earlier than the date of Day 1 study drug administration of its next cycle. For the last cycle (where no subsequent cycle is given), the end of cycle will be defined as Day 7 relative to the last dose of the cycle.

Document: [REDACTED]

Author: [REDACTED]

Version Number:

2.5

Version Date:

18Feb2022

Template No.: [REDACTED]

Reference: CS_WI_BS005

Effective Date: 02Dec2019

Echocardiogram

		Week 12 * (X + 1)	Post-treatment
Visit	Week 12	Week 12 * (X + 1) [b]	
Scheduled Day [c]	85	$1 + 7 * 12 * (X + 1)$	
Echocardiogram	Day 2 to 127	$42 * (2X + 1) + 2$ to $42 * (2X + 3) + 1$ [c]	Last dose date of last cycle +8 to last dose date +37

[a] The scheduled day is relative to the Day 1 of Cycle 1.

[b] X is an intergern starting from 1, and will take maximum value at date of last study drug administration.

[c] The last windowed visit end by the last dose date.

Document:

[REDACTED]

Author:

[REDACTED]

Version Number:

2.5

Version Date:

18Feb2022

Template No.:

[REDACTED]

Reference: CS_WI_BS005

Effective Date: 02Dec2019

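### The SAP closes the post-treatment window 37 days after the last dose, but the protocol times the Treatment Completion visit from the decision to stop, so an on-schedule visit can fall outside the summaries

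*SAP*

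**What the plan says.** **Timing of the visit.** Protocol 6.5 brings the patient back 30 (±7) "days after the decision to permanently discontinue treatment with fruquintinib". Appendix A footnote 3 gives the same anchor, a "follow-up at 30 (±7) days after the decision to discontinue treatment permanently", and SAP Appendix 1 reproduces that footnote. The Appendix A column header is looser: 30 (±7) "days after permanent treatment discontinuation".

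**Timing of the analysis.** SAP 5.4 makes the post-treatment window run "from the last dose date + 8 days to the last dose date + 37 days" and uses the last assessment inside it. SAP Appendix 4 repeats this as "Last dose date of last cycle +8 to last dose date +37". For laboratory data, SAP 17.4 states that results "up to 37 days following the last dose of study medication will be used for analysis". SAP 17.5 (ECG) and 17.6 (vital signs) carry the same 37-day limit. The opening of SAP section 17 applies it to the safety evaluation period in general, unless a section specifies otherwise.

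**Schedule that links the two.** Dosing is on Days 1 to 21 of each 28-day cycle (Protocol Table 7). Routine scans fall on Day 1 of a cycle, with a window of one week either side (Protocol 6.4).

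**The concern.** The two documents count from different dates. The SAP's 37 days is 30 + 7 counted from the last dose, while the protocol's 30 (±7) days is counted from the decision. The dates coincide only when the decision falls on the day of the last dose. They separate on an ordinary path, where progression is found on a Day 1 scan after the week off drug, and separate further when a toxicity interruption ends in a decision to stop.

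Two consequences follow. First, end-of-treatment laboratory, ECG and vital-sign values from a fully compliant visit can be left out of the by-visit summaries. For laboratory and ECG data they can also be left out of the shifts to the worst post-baseline result. Second, assessments at the decision visit itself, at last dose +8, fall on the first day of the post-treatment window. If the real completion visit is outside, the decision-visit values can become the reported post-treatment values. The omission is not random: it depends on how long the patient had been off drug when the decision was made.

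**Working it through.** **Inputs**
- Last scheduled dose: Day 21 of 28 (Protocol Table 7).
- Routine scan and next cycle start: Day 29 counted from the start of the same cycle, which is Day 1 of the next (Protocol 6.4).
- Completion visit: decision +23 to +37, nominal +30 (Protocol 6.5; Appendix A footnote 3).
- SAP window: last dose +8 to +37 (SAP 5.4; Appendix 4).

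**The SAP's own limits**
- Upper: 30 + 7 = 37, which assumes that the visit is counted from the last dose.
- Lower: 29 − 21 = 8, the gap from the Day 21 dose to the next Day 1. Appendix 4 agrees, since it ends the last cycle 7 days after the last dose.

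The lower limit therefore allows for the week off drug. The upper limit does not.

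**Re-anchoring on the decision.** Let g be the days from last dose to decision. The visit is nominally at last dose + g + 30, with a permitted range of g + 23 to g + 37 (15 days). For g from 0 to 15, permitted days inside the window number 37 − (g + 23) + 1 = 15 − g, so g days fall outside.

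| Situation | g | Nominal visit | Permitted range | Days inside | Days outside |
|---|---|---|---|---|---|
| Decision on last-dose day | 0 | +30 | +23 to +37 | 15 | 0 |
| Scan and decision 7 days early | 1 | +31 | +24 to +38 | 14 | 1 |
| Day 1 visit 3 days early | 5 | +35 | +28 to +42 | 10 | 5 |
| Day 1 on time | 8 | +38 | +31 to +45 | 7 | 8 |
| Day 1 visit 3 days late | 11 | +41 | +34 to +48 | 4 | 11 |
| Decision after a 14-day interruption | 14 | +44 | +37 to +51 | 1 | 14 |
| Scan and decision 7 days late | 15 | +45 | +38 to +52 | 0 | 15 |

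The nominal visit stays inside only if g is at most 37 − 30 = 7. The whole permitted range stays inside only if g = 0.

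**Echocardiogram.** Appendix 4 maps the Week 12 echocardiogram to Days 2 to 127. Completion visits after an on-time Day 1 stop fall on these study days:
- C2D1 (Day 29): 29 + 23 to 29 + 37 = 52 to 66
- C3D1 (Day 57): 80 to 94
- C4D1 (Day 85): 108 to 122

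All lie inside the Week 12 window. The section 17 limit for the same three patients ends on Day 21 + 37 = 58, Day 49 + 37 = 86 and Day 77 + 37 = 114. The two rules can therefore give different answers for the same echocardiogram.

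**The case against.** The strongest case for the SAP is that a cut-off counted from the last dose is coherent. The same 37 days governs treatment-emergent adverse events, on-study deaths and concomitant medication. If laboratory values at +45 were admitted without comment, they could enter treatment-emergent grading while an adverse event starting that day would not be treatment-emergent. This stands, and the fix has to deal with it.

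Other defences go less far:
- The Appendix A column header, read as last dose, would give +23 to +37 and fit the SAP exactly. Footnote 3 and section 6.5 both name the decision, so the header needs aligning but does not remove the mismatch.
- SAP 5.3 presents nominal visits, but 5.4 bases visit summaries on windowed visits. The remark in 5.4 on placing a premature visit gives no rule. Neither overrides the limits in 17.4 to 17.6.
- All data appear in listings. That is true, so nothing is lost from the record, but listings do not feed the summary tables.

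A reader might infer more than the documents support:
- **That early stoppers lose their only on-study LVEF value.** The Week 12 echocardiogram window may capture it. The note ending the last windowed visit at the last dose is attached to the later windows, and 17.8.2 sets no cut-off. Against that, the section 17 period may exclude it. The text does not settle the question.
- **That a number of affected patients can be projected from PFS medians in earlier fruquintinib trials.** Such a figure counts progressions and deaths before week 12. It includes patients who die and have no completion visit, patients who do not stop at a scan, and visits that still fall within +37.
- **That counts of the LVEF category of special interest change.** SAP 17.2.6 builds it from reported preferred terms, not from echocardiogram values.

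**Conclusion.** The mismatch is real for laboratory, ECG and vital-sign data. For a patient who takes the Day 21 dose and stops on an on-time Day 1, the nominal completion visit is one day past the limit, and 8 of 15 compliant days are outside it. When the decision comes 14 days after the last dose, 14 of 15 are outside. These are counts of permitted calendar days, not of patients or probabilities. The documents do not say how many patients stop on Day 1 or when within the window visits take place. A visit held before its nominal day, or following an early scan or decision, can still be included.

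Substitution of the decision-visit value at +8 follows from the window's lower limit and the last-assessment rule. It requires that no later assessment fall inside the window. For LVEF the defensible conclusion is only that the SAP's rules are ambiguous.

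The study is descriptive, and no primary endpoint, DLT result or treatment-emergent adverse event count is affected. The point should still be corrected before the tables are produced, because it concerns compliant safety data already collected.

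**What to change.** - In SAP 5.4 and Appendix 4, identify the post-treatment visit by its Treatment Completion label on the CRF, or end its window 37 days after the date of the decision to stop.
- Align SAP 17.4, 17.5, 17.6 and the general period at the start of section 17 so that this visit is included.
- State that an assessment at the decision visit may not stand in for the completion visit.
- State which rule places the completion echocardiogram: the Week 12 window, the post-treatment window or the section 17 period.
- Flag values taken more than 37 days after the last dose, or after the start of new anti-cancer therapy. State whether flagged laboratory values count as treatment-emergent, so that they stay consistent with the adverse-event window, which need not change.
- Align the Appendix A column header with footnote 3 and section 6.5.

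The cost is SAP wording, a small programming change and a clarification of the protocol header. No new data are needed. The downside is small: some summarised values will lie later after the last dose, and the flag makes them visible.
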